### Study Synopsis

Brain signals may be used to control extracorporeal devices such as robotic effectors, prosthetic limbs, or computer systems. For paralyzed patients, a device which implements such a possibility could represent an important step forward in providing some independence and the ability to interact with the environment. This prospective, longitudinal, single-arm feasibility study will be used to evaluate the safety and effectiveness of the Neural Prosthetic System (NPS), a device designed to record brain signals from the cortex, to control physical and virtual effectors. The NPS uses electrodes which are already approved by the FDA for implantations of less than 30 days; an Investigational Device Exemption has been obtained from the FDA which allows implantation of 53 weeks in two subjects. While the NeuroPort Array has been used in other longitudinal clinical studies with similar applications, the primary advantage and differentiating feature of our study is that we will use the posterior parietal cortex to extract cognitive brain signals representing intention and planning of reaching and grasping. This study is not intended to provide immediate treatment or benefits to its participants. However, the long-term implications of the study objectives could enable new technologies to provide assistance to people suffering from paralysis.

NPS Feasibility Study	
Test Device	Neural Prosthetic System, consisting of two NeuroPort Arrays (Blackrock Microsystems, Salt Lake City, UT)
Cohort	People with high cervical spinal lesion (i.e., C4 or above)
Primary Objectives	To assess the safety and evaluate the effectiveness of the NPS as a method for paralyzed people to interact with their environment.
Device Configuration	The NPS consists of two NeuroPort Arrays. Each NeuroPort Array consists of an electrode array (100 electrodes in a 10 x 10 configuration with dimensions 4 mm x 4 mm x 1.5 mm (W x H x D); a titanium percutaneous connector, 19 mm diameter at the base.
Study Design	A longitudinal clinical feasibility study. Subjects participate in study sessions 3-5 times per week at RLANRC (their place of normal clinical care) during the study period. Each subject participates for a total of 66 weeks, including surgeries and follow-up care; the study period is 53 weeks.
Number of Subjects to be Enrolled	Two subjects will be enrolled.
Number of sites	One site, with multiple supporting institutions.
Key Inclusion Criteria	Paralysis (high cervical spinal lesion, C4 or above) initiated at least one year prior and stable for at least 3 months prior.
Key Exclusion Criteria	Active psychiatric or medical illness which precludes surgery, stable participation in study sessions, or which requires MRI or other contraindicated procedure during time enrolled.
Primary Efficacy Objective, Analysis, and Methods	The primary effectiveness objective is to evaluate the long-term effectiveness of the NPS. The primary outcome variable is the accuracy with which tasks are performed during study sessions, which will be compared to the level of chance. The secondary outcome variable is scoring on the Action Research Arm Test, a standard test used in occupational therapy to measure upper extremity limb function following cortical damage. The tertiary outcome variable is the quality-of-life index, measured before and after the study.
Primary Safety Objective, Analysis, and Methods	The primary safety objective is to evaluate the safety of the NPS. The primary outcome variable is the presence of infection or irritation around the implant site. The secondary outcome variable is the Severe Adverse Event (SAE) rate measured per subject as a percentage of implant-days. These factors will be measured during clinical follow-up care using standard observations and exams.

## 1.0 Background and Hypothesis

### 1.1 Clinical Target

The number of patients suffering from some form of paralysis in the United States alone has been estimated to be from 1.7 million (U.S. Dept. Health Human Serv. 1995) to 5.6 million (Christopher & Dana Reeve Found. 2009). Paralysis can result from spinal cord lesion and other traumatic accidents, peripheral neuropathies, amyotrophic lateral sclerosis, multiple sclerosis, and stroke. Another 1.4 million patients have motor disabilities due to limb amputation (U.S. Dept. Health Human Serv. 1995). A majority of these patients still have sufficiently intact cortex to plan movements, but they are unable to execute them. Thus they are candidates for assistance using cortical neural prosthetics.

Many studies have extracted motor execution signals from motor cortex in nonhuman primates and decoded them to predict and/or effect desired movements of a physical or virtual effector. In these studies, it was often observed that the monkeys quickly learned that they did not need to actually move their limb to bring a cursor or device under brain control. We refer to this as cognitive control, in which brain signals not directly related to executing a movement can nonetheless be harnessed for the task. This control can be derived from motor imagery, planning, attention, decision making, or executive control, to name just a few of the cognitive signals that are potentially useful for neural prosthetics. The distinction is not the brain location of the recording but rather the type of signal that is being extracted. Cognitive neural prosthetics tap into brain signals that are neither motor execution commands nor sensory signals, but rather represent higher brain functions such as intention, multi-effector and sequential movement planning, attention, decision making, executive control, emotions, learning, and speech. Scientific understanding of the functional organization of cortex helps to guide the placement of electrodes and the choices of decoding algorithms.

Once decoded, neural signals can be used to control extracorporeal devices such as robotic effectors, prosthetic limbs, or computer systems. Recently, the BrainGate study demonstrated cortical control of a computer cursor in human subject tests with severely paralyzed individuals. This milestone study marked a significant advance in the feasibility of neuromotor prostheses. However, the results obtained in that study (now in a second phase of clinical trials, called BrainGate2) decoded motor execution signals, which is slower than decoding movement goals and other high-level cognitive movement processes.

### 1.2 Study Overview

The proposed study is investigator-initiated and led by [name] at Caltech. The device being tested is the Neural Prosthetic System (NPS), which consists of two microelectrode arrays (NeuroPort Array, Blackrock Microsystems, Salt Lake City, UT) to be implanted in the brain and two sets of recording electronics (NeuroPort Biopotential Signal Processors, Blackrock Microsystems, Salt Lake City, UT) to amplify and record the neural signals. One microelectrode array will be implanted in Brodmann's area 5 (BA5), and the other will be implanted in the anterior intraparietal (AIP) area. The NeuroPort Arrays, which are currently FDA-approved for implantations of less than 30 days, will be implanted for a period of 53 weeks. Two subjects will be enrolled into the study. The NPS will be used to allow study participants to control virtual and real world objects using imagined movements of their arms and hands. While the NeuroPort Array has been used in other longitudinal clinical studies with similar applications, the primary advantage and differentiating feature of our study is that we will use the posterior parietal cortex to extract cognitive brain signals representing reach intention and planning. Therefore, the novelty in our study is twofold: (1) implantation for longer than 30 days, and (2) implantation into the posterior parietal cortex.

### 1.3 Background and Review

#### 1.3.1 Chronic Implantation of NeuroPort Arrays in Humans

The NeuroPort Array is currently under 510(k) clearance by the FDA for human implantations to record and monitor neural activity for less than 30 days. The device has been cleared under IDE status to be chronically implanted in humans as part of the BrainGate and BrainGate2 clinical studies (1-8). The first subject (S1) of the Braingate clinical trial was implanted in June 2004, after three years of paralysis, with a NeuroPort Array located in the M1 arm area, with no reported incidence of adverse events during surgery or post-operative care (2, 8). A second subject (S2) was implanted in which electrical contacts had to be repaired, which caused a delay of 7 months before recording could begin, and was a possible cause for signal loss at month 11 (2). In both subjects,

multiple units were recorded (S1:  $26.9 \pm 14.2$  units; S2:  $53.2 \pm 6.3$  units) over several months well after the 30-day post-implantation mark (2). Over the course of nine months after implantation, S1 learned to use neural activity to perform a variety of daily tasks such as opening email and operating a television (2, 8). A third subject (S3), enrolled nine years after brainstem stroke, and a fourth subject (S4), enrolled six years after being diagnosed with amyotrophic lateral sclerosis (ALS), learned to use their neural activity to control a computer cursor over the course of 1003 days (S3), or 231 days (S4), after implantation (3-8).

In the BrainGate studies, NeuroPort Arrays have been implanted in the left precentral gyrus, in the M1 arm area knob. It is well known from nonhuman primate work that neurons in this region process arm reaching trajectories (9, 10); however, an important result of the BrainGate studies is that despite paralysis in the subjects, this cortical area has continued to process movement trajectories. Furthermore, in recent results documenting performance of online, closed-loop brain control 1000 days after implant, a subject achieved greater than 90% success rates while moving a cursor to targets on a screen (7). These results suggest that neural interfaces can (i) operate successfully over years; and (ii) provide sufficient performance to interact with computers in meaningful ways (2, 6, 7).

### 1.3.2 Posterior Parietal Cortex

In both nonhuman primates and humans, parietal cortex is traditionally thought to lie in the dorsal visual pathway encoding either spatial localization (11), or, alternatively, visual guidance of action (12). The posterior parietal cortex (PPC) is located between the occipital lobe (visual cortex) and postcentral gyrus (somatosensory cortex), and thus is naturally situated to process sensory inputs and project outputs to motor and pre-motor areas (13). Such high-level, multimodal processing of sensory inputs and motor outputs is one reason why we consider these signals as ideal candidates for cognitive control of neural interfaces: whereas motor cortex executes limb movement trajectories, the PPC processes plans which are then transferred to motor cortex for execution (14). Moreover, recent research suggests that PPC can provide a larger degree of useful prosthetic control signals as a result of its being situated at the interface between sensory and motor systems.

The posterior parietal cortex (PPC) is involved in transforming sensory inputs into plans for action – so-called sensory-motor integration (15-17). It is separated by the intraparietal sulcus into the superior parietal lobule and the inferior parietal lobule. Within the intraparietal sulcus, subregions have been implicated in planning eye movements (lateral intraparietal area, LIP) (18), reach movements (parietal reach region, PRR, medial posterior bank of intraparietal sulcus comprising both medial intraparietal (MIP) and V6a areas) (19), and grasping (the lateral anterior intraparietal area, AIP) (20). Brodmann's area 5 occupies the superior parietal lobule, and neurons within that area are active during sensory-motor integration and motor planning for reaches (13, 21-24). In particular the dorsal aspect of area 5 (area 5d) has been implicated in reach planning (25). The high-level, abstract nature of signals in these cortical areas is underscored by observations that plans can be formed and cancelled without execution (15, 26, 27), and that intended reach activity in PRR is coded in visual rather than limb coordinates (28). In contrast, area 5d, which is believed to be positioned downstream of PRR, codes reaches largely in limb coordinates (29, 30). PRR, AIP, and BA5 are particularly relevant to this application because reaching, grasping, and sensory integration for planning and guidance of these movements are integral components for the control of brain-machine interface effectors.

Local field potentials (LFPs) are a continuous signal representing the sum of electrical activity in the brain tissue near an electrode. We have shown that temporal structure in LFPs varies with planned or executed motor behavior (31), and found similar structure in LFPs recorded from LIP during saccade planning (32). Furthermore, we have shown that LFPs can support neural interface decodes as well as neuronal spiking (33-35), and in fact provide signals that are complementary to spikes. LFPs recorded from PPC encode behavioral state with fewer channels than spikes, whereas spikes provide direction of reach information with fewer channels than LFPs (31). Because LFPs are a summed signal, they may be less susceptible to degradation due to scarring (34, 36). Furthermore, LFPs are more robust to array micro-motion (e.g., from sneezing), which can affect single unit sorting assignments. Because of their stability, consistency, and potential for contributing to a neural interface, these signals may be a useful component of neural control.

In human as in monkey, a number of PPC subregions have been identified which are activated for visually guided actions such as reaching and grasping. Some of these areas, based on cytoarchitectural, neuroimaging, and neuropsychological data, have been tentatively identified as homologues of well-studied nonhuman primate areas PRR, AIP, and BA5 (37-51). The activity of human PPC appears to retain desirable qualities of monkey PPC which make this cortical area an ideal candidate for cognitive neural prostheses (40, 43). Neuroimaging studies

with human subjects have demonstrated that activity within the posterior parietal cortex, including areas accessible by the NeuroPort Array along the intraparietal sulcus, can be used to decode reach and grasp activities (50).

### 1.3.3 Adverse Information

Implantation of the NeuroPort Array requires a craniotomy; blunt dissection of the arachnoid space to separate the dura mater from the skull; incisions in the dura mater, and, finally, cortical insertion through the pia mater. During insertion, electrodes penetrate the neural tissue and cause local edema in the brain tissue. These features are common to many styles of electrodes which are designed to record the activity of single units from within the cortex, and so studies of other penetrating electrodes may be useful in understanding mechanisms in play when the NeuroPort Array is implanted. Acutely, local edema and hemorrhage are observed after implantation; these effects heal within weeks (52). Over the first several months, the tissue response to intracortical electrodes is a compact cellular sheath containing astrocytes and microglia (53). Persistent inflammatory reaction may be responsible for a reduced density of neurons in the region of tissue near the electrode (52-54). This phenomenon is not unique to microelectrodes for recording neural activity; it also occurs around the shank of electrodes used for deep brain stimulation (55). The foreign body response has been implicated as one factor in a reduction of recording performance over time for neural implants (52). This scarring tissue may contribute to varying degrees of electrical isolation of implanted electrodes from tissue, reducing the sensitivity of the electrode to biopotential signals generated in the surrounding cortex. One study using CerePort Arrays found a decline in the amplitude of action potential signals of 2.4% per month over as many as 31.7 months in three animals (56). These factors represent a challenge for neural interfaces and for this study. Importantly, despite these factors, it appears that neural interface control with chronic CerePort or NeuroPort Array implantations is still possible (7, 56). None of the authors of these studies indicate whether their investigations were conducted under GLP.

### 1.3.4 Summary of Background Material

The large body of work describing the nature of PPC activity in both nonhuman primate and humans during reaching and grasping leads to several conclusions regarding its value for brain-machine interfaces:

- Decodes of goals are very fast, in the order of 100 ms, which provides more rapid goal acquisition than primary motor cortex (14).
- Trajectories can be decoded with similar fidelity to M1 (57-59).
- At least two sequential goals can be represented and this feature can augment decoding performance of sequential limb movements (60)
- Goal and trajectory information when combined provide better decoding of trajectories than trajectory information alone (57).
- The representation of bilateral arm movements within a single hemisphere can provide bimanual control from a single implant (61, 62).
- The anterior intraparietal area (AIP) represents grasp shape which may reduce the number of cells needed to decode grasping (63, 64).
- PPC has stronger local field potential (LFP) signals than motor cortex (65) and LFPs can provide robust information on behavioral.

In short, cognitive signals in PPC which perform multimodal sensory-motor integration are ideal candidates for control signals in paralyzed patients (14, 34, 66, 67). Moreover, PPC can provide not only the signals found in motor cortex, but also high-level cognitive motor control signals, particularly those related to the goals of movement. One advantage of this multiplicity of signals is that a single implant can allow for a wider variety of control variables thereby improving the range and effectiveness of prosthetic control.

## 1.4 Risk Analysis

This early feasibility study is intended to evaluate the safety and effectiveness of the NPS, and thus is not intended to immediately provide the full benefits of direct brain-control of a prosthetic device to the subjects. The most serious risks to the subjects include those associated with anesthesia, brain surgery, and infection around the percutaneous connector. However, we believe the long-term benefits of the study outweigh the risks to the subject. This section will present an analysis of the risks to the subject associated with this study, specific plans to mitigate these risks, and benefits expected to be derived from this study.

This study will include two (2) subjects (selection criteria outlined in Section 5.0). It is expected that a caregiver will be available and involved in daily wound care and monitoring of the subject's wellbeing.

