- Intracranial hemorrhage, subdural hematoma, or epidural hematoma could result in headache, seizures, stroke, temporary or permanent neurologic impairment such as weakness, sensory loss, or coma, change in consciousness, or death. The expected frequency of these complications is low: reports of neurosurgeries for the treatment of epilepsy or implantation of deep brain stimulators suggest that the incidence of bleeding may be between 0.8% and 3.9% (79-85, 87-90). The surgery will be performed by trained and board-certified neurosurgeons in a controlled medical environment. Major blood vessels will be avoided when the NeuroPort Array is implanted. The subject's vital signs will be closely monitored during the entire procedures to watch for signs of surgical complications. The appropriate equipment and personnel will be available in the operating room to respond to any complications due to anesthesia. The

surgery will be performed according to the surgical manual included in the 510(k) application for the NeuroPort Array. During the first two days of post-operative recovery period at USC the patient will undergo a CT scan to ensure that there is no bleeding from the device implantation procedure. The patients will be placed on Keppra 500 mg PO q12 hours for two weeks for routine seizure prophylaxis.

- Cerebrospinal Fluid (CSF) leakage during the surgery could result in a dull or throbbing headache or need for additional surgery, and could be a factor for increased risk of infection. The expected frequency of these complications is low. Evidence from the literature suggests that CSF leakage occurs in a low percentage of neurosurgeries: in epilepsy-related procedures, for example, the incidence of CSF leakage has been reported from 0.1% to 1.4% (88, 89). CSF leakage has been implicated as a potential factor for increased risk of infection (74). Subjects will be monitored closely intraoperatively and during post-operative critical care and throughout the study to watch for signs of CSF leakage. The attending physician will medicate pain as determined medically necessary, and will determine the appropriate response if medication is insufficient.

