10.0 Criteria for Evaluation and Endpoint Definitions

The objectives of this study are to evaluate the safety and effectiveness of the NPS. Each of these objectives will be measured quantitatively as defined in Table 10-1 and described in this section.

Table 10-1. Safety and Effectiveness Endpoints

Objective	Hypothesis	Method of Evaluation	Time of Assessment	Comparisons Made
To evaluate the safety of the NPS implant	Primary endpoint – implantation will not be associated with infection or irritation	Inspection of subject's scalp for evidence of reddening or discharge; review of new symptoms including possible fever, headache, visual or auditory changes, or change in mood or behavior; serial neurologic exams	Immediately after implantation and weekly thereafter	The condition of the area will be compared with its condition on previous visits  History will be obtained regarding new symptoms  Neurologic exam will be compared to baseline neuro exam
	Secondary endpoint – the Severe Adverse Event (SAE) rate will not rise above 1% for any study subjects.	The SAE rate will be calculated as the number of SAEs per implant-days.	The SAE rate will be available on a daily basis throughout the study.	The SAE rate will be continuously compared to the 1% threshold level.
To evaluate the effectiveness of the NPS	Primary endpoint – patient control over the end effector (virtual or physical), as measured by accuracy, will be significantly greater than chance when using the NPS	Calculated by the NPS computer apparatus	At the end of every study session	Assessments will be compared with chance
	Secondary endpoint – Action Research Arm Test (ARAT) scores will improve over the course of the trial when controlling the virtual or physical robotic arm	ARAT administered by occupational therapists	At 10-week intervals starting at week 3.	Scores will be compared to the baseline, i.e., the first score from week 3.
	Tertiary endpoint – using the NPS with either a virtual or physical end effector will result in significant increases in the subject's quality of life	Quality of Life Inventory (QOLI) administered by the NPS operator	During prescreening (baseline) and every month subsequent to implantation	Monthly QOLI score will be compared against baseline

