## 10.1 Safety Endpoints

### 10.1.1 Infection and Irritation

Infection and irritation are the most serious risks identified for the NPS, and as such the absence of both serves as a primary safety endpoint for the study. The implant sites will be monitored by visual inspection of the wound margin, verbal survey of the subject, and neurologic exam.

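### The primary safety endpoint counts only infection and irritation, on a risk ranking that Section 1.4 contradicts; no non-infectious bleed, stroke, lasting deficit or death fails it, and the SAE rate is only a partial backstop

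*Protocol*

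**What the plan says.** Section 1.4 of the protocol groups three sources of risk at the top: "The most serious risks to the subjects include those associated with anesthesia, brain surgery, and infection around the percutaneous connector". Section 1.4.1 attributes most of the risk to the implant and explant surgeries together with the connector. Section 1.4.2 spells out the surgical harms: "Intracranial hemorrhage, subdural hematoma, or epidural hematoma could result in headache, seizures, stroke, temporary or permanent neurologic impairment", and goes on to coma and death.

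Section 10.1.1 gives a different ranking and makes it the reason for the endpoint: "Infection and irritation are the most serious risks identified for the NPS, and as such the absence of both serves as a primary safety endpoint".

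Every statement of the endpoint has the same scope. The synopsis says: "The primary outcome variable is the presence of infection or irritation around the implant site". Table 10-1 says: "Primary endpoint – implantation will not be associated with infection or irritation". Sections 1.5 and 2.1 agree. The same row of Table 10-1 lists symptom review and serial neurologic exams as methods, with the comparison "Neurologic exam will be compared to baseline neuro exam", but attaches no failure criterion to a neurologic change.

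The secondary safety hypothesis is that "the Severe Adverse Event (SAE) rate will not rise above 1% for any study subjects". It is computed as SAEs per implant-day, is available daily, and is compared with the threshold continuously. The SAP reproduces Section 13 of the protocol and defines no safety endpoint.

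**The concern.** The reason given for the endpoint conflicts with the protocol's own risk analysis. Skin irritation is inside the primary endpoint but does not appear in the Section 1.4 ranking. Operative harm is in that ranking but outside the endpoint. A reddened scalp can therefore count against the primary safety hypothesis, while a fatal stroke without infection cannot.

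Safety is the study's first objective, and Section 13.4 uses the two subjects' outcomes to judge whether larger studies are warranted. A primary safety result reported as met would then say nothing about the gravest harms the protocol describes. The question is how far the secondary endpoint makes up for this.

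**Working it through.** The plan gives no power, alpha or sample-size figure for this endpoint, so there is nothing to reproduce. The check has three parts.

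**1. What can fail the primary hypothesis.** The five statements (synopsis, 1.5, 2.1, Table 10-1, 10.1.1) all name infection or irritation only. Section 10.1.1 uses the neurologic exam as one way of monitoring the implant sites. No text says that a non-infectious bleed, stroke, deficit or death fails the hypothesis.

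**2. What the SAE rate catches.** Inputs: 53 weeks of implantation (Section 3.1), or 53 × 7 = 371 days; threshold 1% (Table 10-1). Rate on implant-day d after k SAEs = k/d. The endpoint is worded as *severe* and Section 8.2.1 defines *serious* events; I assume they are the same.

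- One SAE at implantation, counted on day 2: 1/2 = 50%. Breach.
- One SAE by day 99: 1/99 = 1.01%. Breach.
- One SAE on day 100: 1/100 = 1.00%, which is not above 1%. No breach.
- One fatal stroke on day 120: 1/120 = 0.83%. No breach.
- One bleed at the planned explantation: about 1/371 = 0.27%. No breach.
- End of implantation: 0.01 × 371 = 3.71, so 3 SAEs pass (3/371 = 0.81%) and 4 fail (4/371 = 1.08%). To pass throughout under continuous comparison, the three must fall no earlier than days 100, 200 and 300 respectively.
- With 52 weeks, as in the calendar in Section 18.1 (364 days), the limit is also 3 (0.01 × 364 = 3.64).

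The rate does not weigh severity. Under 8.2.1 an admission of less than 24 hours for an adverse event counts the same as a death.

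**3. How likely such events are.** Chance of at least one event in n exposures = 1 − (1 − p)^n, with the rates cited in Section 1.4.2 and independence assumed.

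| Event | p | n | Chance |
|---|---|---|---|
| Bleed, one exposure per subject | 0.8% to 3.9% | 2 | 1 − 0.992² = 1.6% to 1 − 0.961² = 7.6% |
| Bleed, all four operations | 0.8% to 3.9% | 4 | 1 − 0.992⁴ = 3.2% to 1 − 0.961⁴ = 14.7% |
| Permanent deficit, one exposure per subject | 0.6% to 1.5% | 2 | 1 − 0.994² = 1.2% to 1 − 0.985² = 3.0% |

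The four-operation row assumes that the range applies to each operation, explantation included. The protocol does not say so: the figures come from epilepsy surgery and deep brain stimulator implantation, and Section 1.4.1 gives its epilepsy-lead hemorrhage rate per patient.

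**The case against.** **The rankings can be partly reconciled.** Section 1.4 speaks of risks to the subjects, and 10.1.1 of risks identified for the device. Section 1.4.3 calls infection the main risk to subjects, and 8.1.1 calls it the main long-term risk of the device. This explains why infection is prominent. It does not remove the conflict: 1.4.3 goes on to name anesthesia and surgery as further significant risks, and the device cannot be evaluated without the two operations.

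**The SAE rate covers operative harm.** This stands in part. A reader might infer that an implant-surgery bleed also slips past the secondary endpoint because one event over the full period is only 0.27%. The documents do not support that. The comparison is continuous, so an SAE in the first days puts the rate far above 1%, and it stays above 1% until day 100. The 0.27% figure fits an event at explantation, not one at implantation.

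**These harms are already watched and acted on.** This is true. Neurologic exams and symptom review are scheduled. Hematoma requiring evacuation, onset of epilepsy, significant change on neurologic exam and serious adverse events are withdrawal criteria in 5.3. Section 8.2.3 requires all adverse events to be recorded. A reader should not infer that such events would go unseen. But withdrawal criteria and event records do not decide whether the primary hypothesis is met.

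**Two subjects and no formal decision rule.** Section 13.4 disclaims conclusions on absolute safety and looks to the subjects' outcomes generally, not to the primary result alone. This lowers the stakes but does not make the result informative.

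**Counting every hemorrhage would overreach.** This stands. Section 1.3.3 says local hemorrhage is seen after insertion and heals within weeks, and each subject has a postoperative CT. Any added component needs a threshold.

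**Conclusion.** The point holds in a limited form. Sections 1.4 and 10.1.1 disagree on the ranking that justifies the primary safety endpoint and must be reconciled. No non-infectious hemorrhage, stroke, persistent deficit or death fails the primary hypothesis as written. The remaining gap in the secondary endpoint is a lone SAE from implant-day 100 on, including one at explantation: with no infection or irritation, that subject meets both safety hypotheses.

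The chances are modest: 1.6% to 7.6% for at least one bleed in two subjects and 1.2% to 3.0% for a permanent deficit, at rates borrowed from other procedures, with one exposure each and independence. The 3.2% to 14.7% figure for bleeding needs the further assumption of four equal exposures. These are chances of events the primary endpoint ignores. They are not chances of passing both endpoints, since some of the events would come early enough to breach the SAE rate. The case for change rests on the gravity of the events and the low cost of the repair.

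**What to change.** In the synopsis, 1.5, 2.1, Table 10-1 and 10.1.1, define the primary safety endpoint as two separately reported parts:

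- (a) infection or irritation, as now;
- (b) death, or any intracranial hemorrhage, stroke, seizure or persistent new neurologic deficit that meets the serious adverse event definition in 8.2.1, from implant surgery to the three-month post-explant visit.

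State that the primary safety hypothesis is met only if neither part occurs. Tying (b) to 8.2.1 means that the local hemorrhage described in 1.3.3 does not count by itself. Correct the rationale sentence in 10.1.1 so that it agrees with 1.4.

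Cost: no new assessments. CT follows both operations (3.6, 3.9), neurologic exams run to the three-month post-explant visit (8.1.2, Section 18.1), and adverse events are already recorded (8.2.3). The downside is that the primary safety hypothesis becomes somewhat less likely to be met.
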